2.4.2 Prior, concomitant and post therapies

Prior anti-cancer therapy

The number and percentage of patients who received any prior anti-neoplastic medications, prior anti-neoplastic radiotherapy or prior anti-neoplastic surgery will be summarized by cohort. Prior anti-neoplastic medications will be summarized by therapy type (e.g. chemotherapy, hormonal therapy etc.), setting (e.g. adjuvant, metastatic, etc.) and also by lowest ATC class, preferred term and treatment. Summaries will include total number of regimens, best response and time from last treatment to progression for the last therapy.

The medication therapy type of any combination therapy will be classified based on the following order: chemotherapy, biologic therapy, targeted therapy, hormonal therapy. For example, a combination therapy of chemotherapy and hormonal therapy will be classified as 'chemotherapy'. For radiotherapy, locations and setting of last therapy will be summarized. For prior surgery, time since last surgery, procedure and residual disease of last therapy will be summarized.

In addition, number (%) of patients who received any hormonal therapy (irrespective of given in combination with chemotherapy or biologic or targeted therapy), any aromatase inhibitors, any hormonal therapy other than aromatase inhibitors in any setting and in the metastatic setting, any prior CDK4/6 inhibitors will be summarized by cohort.

Separate listings will be produced for prior anti-neoplastic medications, radiotherapy, and surgery.

Anti-neoplastic medications will be coded using the WHO Drug Dictionary (WHO-DD); anti-neoplastic surgery will be coded using MedDRA. Details regarding MedDRA and WHO-DD version will be included in the footnote in the tables/listings.

The above analyses will be performed using the FAS .

Post treatment anti-cancer therapy

Anti-neoplastic therapies since discontinuation of study treatment will be listed and summarized by ATC class, preferred term, by cohort by means of frequency counts and percentages using FAS.

Concomitant medications

Concomitant therapy is defined as all interventions (therapeutic treatments and procedures) other than the study treatment administered to a patient coinciding with the study treatment period. Concomitant therapy include medications (other than study drugs) starting on or after the start date of study treatment or medications starting prior to the start date of study treatment and continuing after the start date of study treatment.

Concomitant medications will be coded using the World Health Organization (WHO) Drug Reference Listing (DRL) dictionary that employs the WHO Anatomical Therapeutic Chemical (ATC) classification system and summarized by lowest ATC class and preferred term using frequency counts and percentages. Surgical and medical procedures will be coded using MedDRA and summarized by SOC and preferred term. These summaries will include:

- Medications starting on or after the start of study treatment but no later than 30 days after start of last dose of study treatment and
- Medications starting prior to start of study treatment and continuing after the start of study treatment.

All concomitant therapies will be listed. Any concomitant therapies starting and ending prior to the start of study treatment or starting more than 30 days after the last date of study treatment will be flagged in the listing. The safety set will be used for all concomitant medication tables and listings.

According to the study protocol Table 14-2, treatment with substances which are strong CYP3A inhibitors, or inducers of CYP3A or medications with a known risk of QT prolongation should be avoided. However, some patients may take these substances during the treatment period so these concomitant medications will be selected via programming and tabulated and listed in the Clinical Study Report. Treatment with the prohibited substances mentioned above will be identified in the database as protocol deviations.

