6.4.4 Prohibited concomitant therapy

The following medications are prohibited during treatment in this study (see Table 14-2 and Table 14-3 in Appendix 1), this list is not comprehensive and is only meant to be used as a guide. Please contact the medical monitor with any questions:

- Strong inducers of CYP3A4: Avoid co-administration of alpelisib with a strong CYP3A4 inducers as it could potentially reduce the effectiveness of alpelisib (see Table 14-2).
- Inhibitors of Breast Cancer Resistance Protein (BCRP) efflux transporter: Avoid the use of BCRP inhibitors in subjects treated with alpelisib (see Table 14-3). If unable to use alternative drugs, closely monitor for increased adverse reactions.
- Other investigational and antineoplastic therapies

.

Agents required for managing adverse events, cancer symptoms, and supportive care agents, such as anti-emetics, anti-diarrheal and probiotics are allowed unless listed above and/or in Appendix 1.

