14.1.2 Prohibited Medication

Strong inducers of CYP3A4

This list of CYP inducers was compiled from the University of Washington's Drug Interaction Database (Updated Nov-2020). This list only meant to be used as a guide.

Table 14-2 List of prohibited strong inducers of CYP3A4

Category	Drug Name
Strong CYP3A Inducers	Apalutamide, Avasimibe ¹ , Carbamazepine, Enzalutamide, Ivosidenib, Lumacaftor, Mitotane, Phenobarbital, Phenytoin, Rifabutin, Rifapentine, Rifampin (Rifampicin), St. John's wort (hypericum perforatum) ¹

¹ Herbal product

Inhibitors of BCRP

The table encompasses only drugs and molecular entities for which inhibition of BCRP has been investigated and/or formally shown in vivo in a clinical DDI study. Please note that this is not an exhaustive list and only meant to be used as a guide. When in doubt, refer to the prescribing information of the drug to assess whether a potential for BCRP inhibition is described.

Table 14-3 List of prohibited BCRP inhibitors

Category	Drug Name
BCRP inhibitors - Evidence for DDI potential shown in vivo	Atazanavir/ritonavir ^{1,2} , Elvitegravir/cobicistat ^{1,2} , Lopinavir/ritonavir ^{1,2} , Tipranavir/ritonavir ^{1,2} Curcumin ^{1,2} , Cyclosporine ^{1,2} , Daclatasvir ^{1,2} , Eltrombopag ^{1,2} , Gefitinib ² , Lapatinib ¹ , Ledipasvir ² , Pantoprazole ^{1,2} , Paritepravir ² , Tipranavir ²

¹ Lee et al 2015

² Novartis PK Sciences DDI List (January, 2018)

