- *Patients do not have either: Measurable disease, at least one measurable lesion as per RECIST v1.1 criteria or If no measurable disease is present, then at least one predominantly lytic bone lesion must be present*
- *Patient has an ECOG performance status greater than 2 or ECOG missing*
- *Patient did not provide main study informed consent*
- *Patient enrolled in the wrong treatment cohort*
- *Patient who has been enrolled but not taken any dose of study drug*
- *Concurrent other anti-cancer therapy, or investigational therapy except palliative therapy, while on study treatment*
- *Concurrent treatment with prohibited drugs as per Protocol which puts patients under significant risk (please refer the Protocol section for Prohibited Medication)*

Safety Set

The **Safety set** includes all patients who received at least one dose of any component of the study treatment. Patients will be analyzed according to the study treatment actually received.

The actual treatment received corresponds to:

1. the assigned treatment if patients took at least one dose of that treatment.
2. the first treatment received if the assigned treatment was never received.

Safety Set in Extension Phase

The **Safety set in Extension Phase** includes all patients who received at least one dose of any component of the study treatment in Extension Phase. Patients will be analyzed according to the study treatment actually received.

The actual treatment received corresponds to:

1. the assigned treatment if patients took at least one dose of that treatment.
2. the first treatment received if the assigned treatment was never received.

Patient Classification:

Patients may be excluded from the analysis populations defined above based on the protocol deviations entered in the database and/or on specific patient classification rules defined in [Table 2-2.](#)

Table 2-2 Patient classification based on protocol deviations and non-PD criteria

Analysis set	Protocol deviations leading to exclusion	Non protocol deviation leading to exclusion
FAS	No written inform consent	No dose of study treatment received.
mFAS	No written inform consent	PI3KCA mutation not confirmed by a Novartis designated laboratory and no dose of study treatment received.
Safety set	No written inform consent	No dose of study treatment
Safety set in Extension Phase	No written inform consent	No dose of study treatment in Extension Phase

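### SAP 2.4.2 keeps a superseded prohibited-drug list: it flags QT-prolonging drugs and strong CYP3A inhibitors and does not isolate BCRP inhibitors

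*SAP*

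**What the plan says.** The concomitant-medication paragraph of SAP 2.4.2 names protocol Table 14-2 as its source and says that "strong CYP3A inhibitors, or inducers of CYP3A or medications with a known risk of QT prolongation should be avoided". Because some patients may still take such drugs, it adds that "these concomitant medications will be selected via programming and tabulated and listed in the Clinical Study Report". It ends: "Treatment with the prohibited substances mentioned above will be identified in the database as protocol deviations".

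The current protocol has different content under that table number: "Table 14-2 List of prohibited strong inducers of CYP3A4". The next table is "Table 14-3 List of prohibited BCRP inhibitors". Section 6.4.4 of the protocol prohibits three things during treatment: strong CYP3A4 inducers, BCRP inhibitors, and other investigational or antineoplastic therapies. On the second it says: "Avoid the use of BCRP inhibitors in subjects treated with alpelisib".

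SAP 2.2 has a separate per-protocol (PPS) exclusion: "Concurrent treatment with prohibited drugs as per Protocol which puts patients under significant risk". That criterion sends the reader to the protocol's section on prohibited medication.

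**The concern.** The paragraph is an operating instruction. It determines which drugs a program selects, what the study report tabulates and lists as prohibited medication, and what is identified as a deviation. If its list is not the protocol's list, the report will show as prohibited some drugs that the current protocol does not prohibit during treatment. It will have no dedicated output for a class that the protocol does prohibit. Section 6.4.4 asks for close monitoring for increased adverse reactions when BCRP inhibitors cannot be avoided, so a reader of the safety results would want that use identified.

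**Working it through.** No arithmetic bears on the main point. The two lists are set side by side.

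| Class | SAP 2.4.2 | Current protocol, on treatment (6.4.4, Tables 14-2 and 14-3) |
|---|---|---|
| CYP3A inducers | Named, without clearly keeping the limit to strong ones | Strong inducers prohibited, Table 14-2 |
| Strong CYP3A inhibitors | Named | Not listed; they appear in exclusion criterion 10, an entry rule |
| QT-prolonging drugs | Named | Not listed |
| BCRP inhibitors | Not named | Prohibited, Table 14-3 (14 entries) |

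One class matches in substance, two are in the SAP only, and one is in the protocol only. The third item in 6.4.4, other investigational and antineoplastic therapy, is also absent from 2.4.2, but SAP 2.2 covers it as a PPS criterion of its own.

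**Which protocol version applies.** SAP Amendment 4 says it is based on protocol V05. The protocol at hand is V06, and the Amendment 6 list of changes does not touch 6.4.4 or Appendix 1. The version change therefore does not explain the difference. The extension-phase SAP refers back to SAP Amendment 4 for all main analyses, so the paragraph is still in force.

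**Origin.** The Amendment 4 log (31-Oct-2019) explains the text, although the contradiction itself is between current texts. Before that amendment, Table 14-2 was a list of prohibited QT-prolonging drugs, and BCRP inhibitors were in a table of drugs to be used with caution. Amendment 4 removed the QT list and made BCRP inhibitors prohibited. The SAP history records an update for protocol amendments 3 and 4 on 07-Nov-2019 but no change to this paragraph. SAP section 4, on changes to protocol-specified analyses, deals only with COVID-19. Nothing declares a deliberate departure.

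**How far it reaches.**
- Programmed prohibited-medication table and listing: directly affected, since 2.4.2 defines the selection.
- Deviation flag: affected as 2.4.2 words it. The deviation categories, however, come from the Data Handling Plan (SAP 2.3.2, protocol deviations), which is not among the documents.
- PPS: its criterion refers to the protocol, not to 2.4.2.
- Primary analysis: uses the mFAS, and SAP Table 2-2 excludes no one from it for prohibited medication.

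**Timing.** By 08-Oct-2019, shortly before Amendment 4, 254 patients were enrolled; the final total was 380. 254/380 = 66.8%, so about two thirds of patients entered under earlier protocol versions. One fixed list cannot be right for the whole trial.

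**The case against.** Several points count against a larger claim, and most of them stand.

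- A reader might infer that per-protocol exclusions follow the wrong list. They do not on the documents' wording: the PPS criterion points to the protocol's own section and is limited to use that puts patients at significant risk. An indirect route exists, because SAP 2.2 allows exclusions based on deviations entered in the database, but whether it operates depends on the Data Handling Plan.
- A reader might infer that the deviation counts will be wrong. SAP 2.4.2 says the named drugs will be identified as deviations. It does not say that only those will be, so BCRP use may be coded elsewhere.
- A reader might infer that the safety review will miss BCRP-inhibitor use. All concomitant medication is listed, and it is summarised by ATC class and preferred term on the safety set. The use stays visible by drug name. What is lacking is an output that isolates it.
- Flagging strong CYP3A inhibitors is not always wrong. Under exclusion criterion 10, concurrent use at entry can be a true eligibility deviation.
- Before Amendment 4 a QT flag agreed with the list then in force, and BCRP use was a matter for caution. Simply substituting the current list for all patients would create new errors.

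The last two points shape the fix. None of the five removes the mismatch between the SAP's stated rule and the protocol it cites.

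**Conclusion.** The point holds in this limited form. SAP 2.4.2 attributes to Table 14-2 a list that the table no longer contains. Followed as written, it labels QT-prolonging drugs and on-treatment strong CYP3A inhibitors as prohibited under the current protocol, and it does not isolate BCRP-inhibitor use.

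The mismatch is certain from the texts. Its size in patients is unknown, because the documents give no figures on concomitant use. Inconsistent deviation counts are a risk that depends on the Data Handling Plan and have not been shown to occur. No effect on the PPS is shown, and the PPS analysis is in any case optional and conditional on the mFAS hypothesis being met (SAP 2.5.4). The primary mFAS result does not change. The correction is worth making because it concerns safety and deviation reporting and costs little.

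**What to change.** 1. Before building any look-up list, the sponsor must reconcile two protocol passages. Table 14-3 lists pantoprazole as a prohibited BCRP inhibitor, while section 6.4.1.2 allows co-administration with proton-pump inhibitors if alpelisib is taken after food. The sponsor should also state whether BCRP-inhibitor use under the 6.4.4 clause for cases without an alternative counts as a deviation.
2. Replace the list in SAP 2.4.2 with one that follows protocol 6.4.4 and Tables 14-2 and 14-3, and correct the table reference.
3. Apply the flag by the protocol version in force when the drug was taken. Each amendment needed ethics approval before implementation, so the changeover date differs by site. The earlier protocol versions, which are not among the documents reviewed, have to be consulted for the older lists.
4. Treat strong CYP3A4 inhibitors only as an eligibility deviation under exclusion criterion 10.
5. Confirm that the Data Handling Plan deviation codes use the same list.
6. Leave the PPS criterion unchanged. Replacing it with a bare drug list would lose its limit to significant risk.

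The cost is a short change to one SAP paragraph, a dated look-up list and a check of the Data Handling Plan. No new patient data are needed.

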- 10. Patients being concurrently treated with drugs recognized as being strong inhibitors or inducers of the isoenzyme CYP3A4 or inhibitors of BCRP; switching to different medications prior to entry of treatment phase is allowed within the last 5 days prior to study treatment (see Appendix 1 for complete list).
- 11. Patient has a history of noncompliance to medical regimens.
- 12. Patient with severe liver impairment (Child Pugh score B/C).
- 13. Patient has impairment of gastrointestinal (GI) function or GI disease that may significantly alter the absorption of the study drugs (e.g. ulcerative diseases, uncontrolled nausea, vomiting, diarrhea, malabsorption syndrome, or small bowel resection) based on investigator discretion.
- 14. Patient has documented pneumonitis / interstitial lung disease which is active and requiring treatment (chest CT scan performed at baseline for the purpose of tumor assessment should be reviewed to confirm that there are no relevant pulmonary complications present).
- 15. Patient is concurrently using other anti-cancer therapy. All anti-cancer therapy must be discontinued prior to day one of study treatment. Drugs with overlapping toxicities must be discontinued within 7 days and AE resolved to NCI CTCAE v4.03 Grade ≤1 prior to study treatment. Exception to this criterion: patients with any grade of alopecia are allowed to enter the study.
- 16. Patient has had major surgery within 14 days prior to starting treatment with alpelisib or has not recovered from major side effects.
- 17. Patient has any of the following cardiac abnormalities:
 - Symptomatic congestive heart failure
 - i. History of documented congestive heart failure (New York Heart Association functional classification III-IV), documented cardiomyopathy
 - ii. Left Ventricular Ejection Fraction (LVEF) <50% as determined by Multiple Gated acquisition (MUGA) scan or echocardiogram (ECHO)
 - Myocardial infarction \leq 6 months prior to enrollment
 - Unstable angina pectoris
 - Serious uncontrolled cardiac arrhythmia
 - Symptomatic pericarditis

- Uncontrolled hypertension defined by a Systolic Blood Pressure (SBP) ≥ 160 mmHg and/or Diastolic Blood Pressure (DBP) ≥ 100 mm Hg, with or without antihypertensive medication. Initiation or adjustment of antihypertensive medication(s) is allowed prior to screening.
- 18. History of acute pancreatitis within 1 year of screening or past medical history of chronic pancreatitis.

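### SAP 2.4.2 builds the prohibited-medication table and deviation flag on drug classes that do not match current protocol 6.4.4: BCRP inhibitors are left out, and QT drugs and strong CYP3A inhibitors are put in

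*SAP*

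**What the plan says.** The last paragraph of SAP (Amendment 4) 2.4.2 points to protocol Table 14-2 and says that "strong CYP3A inhibitors, or inducers of CYP3A or medications with a known risk of QT prolongation should be avoided". Drugs in these classes are to be picked out by program, then tabulated and listed in the CSR. It closes: "Treatment with the prohibited substances mentioned above will be identified in the database as protocol deviations". The same section also says "All concomitant therapies will be listed".

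The current protocol reads differently. The table that the SAP cites is headed "Table 14-2 List of prohibited strong inducers of CYP3A4", and the next is "Table 14-3 List of prohibited BCRP inhibitors". Section 6.4.4 bars three groups on treatment: strong CYP3A4 inducers; BCRP inhibitors, with the instruction "Avoid the use of BCRP inhibitors in subjects treated with alpelisib"; and "Other investigational and antineoplastic therapies". Strong CYP3A4 inhibitors appear as a named class in exclusion criterion 10, which concerns patients on "strong inhibitors or inducers of the isoenzyme CYP3A4 or inhibitors of BCRP" at study entry.

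The SAP introduction states that it follows protocol V05. The later Extension Phase SAP (2.1) sends the reader back to SAP Amendment 4 for all main analyses, so the 2.4.2 rule still stands.

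**The concern.** The paragraph is an operative rule: it decides which drugs enter the CSR's prohibited-medication table and which uses are identified as deviations. If it names the wrong classes, the errors run both ways. Use of a drug that the protocol does not prohibit on treatment is reported as a violation, and use of a class that it does prohibit is absent from the table meant to show it.

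The omission has some clinical content. Protocol 1.2.4.3 says that BCRP inhibitors may affect alpelisib elimination, and 6.4.4 asks for close monitoring when they cannot be avoided. A reader of the safety results would want to see how many patients took them. Protocol section 12 also requires significant deviations to be reported in the CSR, so the flags should be right.

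**Working it through.** The plan states no figure to reproduce. The check sets the classes side by side.

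| Class | SAP 2.4.2 | Protocol 6.4.4, on treatment | Other relevant place |
|---|---|---|---|
| Strong CYP3A4 inducers | Yes, as CYP3A inducers | Yes, Table 14-2 (13 entries) | Exclusion criterion 10 |
| Strong CYP3A inhibitors | Yes | No | Exclusion criterion 10, at entry |
| QT-risk drugs | Yes | No | Prohibition removed by protocol Amendment 4 |
| BCRP inhibitors | No | Yes, Table 14-3 (14 entries) | Exclusion criterion 10; SAP 2.2 by reference to the protocol |
| Other investigational or antineoplastic therapy | No | Yes | Named as a deviation in SAP 2.2 |

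1. Overlap: of the SAP's 3 classes, 1 is in 6.4.4. That one is arguably wider in the SAP, because the word strong is attached to the inhibitors and not clearly to the inducers. Nothing turns on this.
2. Omission: of the 3 classes in 6.4.4, 2 are not in 2.4.2. Other antineoplastic or investigational therapy is handled by name among the per-protocol exclusions in SAP 2.2, so BCRP inhibitors are the substantive gap.
3. Timing: the amendment log is used only to date the change. Protocol Amendment 4 (31-Oct-2019) deleted a Table 14-2 of prohibited QT drugs, took QT drugs out of the prohibited section, and moved BCRP inhibitors from caution to prohibited. SAP Amendment 4 is dated 24-Mar-2022, which is 875 days later; 875 / 30.4375 = 28.7 months. Three SAP versions postdate the change (07-Nov-2019, 03-Mar-2021, 24-Mar-2022), and the first was made for protocol amendments 3 and 4. None of their history entries mentions this drug list.
4. A deliberate citation of an old protocol version is unlikely. The SAP gives V05 as its basis, and its ECOG cross-reference (2.8.4.4 to protocol Table 7-4) matches current numbering.
5. Both regimes apply to this study: 254 of 380 patients (254 / 380 = 66.8%) were enrolled by 08-Oct-2019, and 380 - 254 = 126 (33.2%) after that date. Earlier patients still on treatment also moved to the new list. The 2.4.2 paragraph sets no limit by date or protocol version.

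The documents do not say how many patients took any of these drugs.

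**The case against.** Much can be said for the plan, and several parts of it stand.

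- **BCRP use is not outside every rule.** A reader might infer that it would go unrecorded. The documents do not support that. SAP 2.2 excludes from the per-protocol set patients given drugs prohibited by the protocol that put them at significant risk, and it refers to the protocol's own section, which includes BCRP inhibitors. SAP 2.3 tabulates deviations leading to exclusion and lists all deviations. The general listing and ATC summary also remain. What is missing is the class in the 2.4.2 table, and the 2.4.2 flag for use that falls short of significant risk.
- **The Data Handling Plan may govern.** SAP 2.3 takes deviation categories from that plan, which was not supplied. It may be correct. The SAP should still not contradict the protocol.
- **QT drugs belong in part.** They were prohibited before protocol Amendment 4, when about two thirds of patients had been enrolled. A cumulative report needs them for that period. The fault is the missing time limit.
- **Not all of the list is shown to be superseded.** The log shows this for QT drugs only. It shows no earlier on-treatment ban on strong CYP3A inhibitors; the point is only that 6.4.4 contains none now. Appendix 3 does advise against antifungals without a diagnosed infection because they may interfere with alpelisib metabolism, so tabulating CYP3A inhibitors has some use. That advice is not a prohibition of the class.
- **Not every Table 14-3 drug is a violation.** Section 6.4.4 accepts BCRP inhibitors with close monitoring where no alternative exists. Pantoprazole is in Table 14-3, yet 6.4.1.2 allows proton-pump inhibitors with alpelisib taken after food. Coding the table mechanically would create new errors, and 6.4.4 calls its lists a guide.

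**Conclusion.** The point holds as a mismatch between current SAP text and current protocol text. Run as written, the 2.4.2 table omits BCRP inhibitors as a class and counts QT drugs and strong CYP3A inhibitors that 6.4.4 does not prohibit on treatment.

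The consequence is limited to one CSR table and its associated deviation flag. The primary mFAS analysis is unaffected. Per-protocol membership is not shown to change either, because its criterion refers to the protocol rather than to the 2.4.2 list. The 28.7 months and the 66.8% / 33.2% split describe how old the discrepancy is and which patients fall under which regime; they do not measure impact. The conclusion assumes that the Data Handling Plan does not override 2.4.2, which cannot be checked here. It is worth correcting because the rule is explicit and the correction is cheap.

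**What to change.** Replace the last paragraph of SAP 2.4.2 as follows.

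- Select and tabulate according to protocol 6.4.4 with Tables 14-2 and 14-3: strong CYP3A4 inducers, BCRP inhibitors, and other investigational or antineoplastic therapies.
- Handle strong CYP3A4 inhibitors as an entry deviation under exclusion criterion 10.
- Tabulate all BCRP inhibitor use, but code it as a deviation only after medical review, allowing for the 6.4.4 provision where no alternative is available and the 6.4.1.2 permission for proton-pump inhibitors such as pantoprazole.
- Tabulate QT drugs separately, and flag them as deviations only for use before protocol Amendment 4 took effect. The exact rule uses each site's approval date, because that amendment needed IRB/IEC approval before implementation. A single stated cut-off date is simpler.

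The cost is one SAP paragraph, a revised medication search list, a little programming and some medical review. No new data are needed, since Core Phase concomitant medications are already recorded, and the protocol does not change. Site approval dates would have to be mapped to medication records; a single cut-off avoids that at the price of some imprecision around the changeover. If the Core Phase database is already locked, a SAP addendum or a CSR note serves instead.
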